### 6.2.3 End of treatment and follow-up

**End of treatment (EOT) visit:** within 5 calendar days after permanent termination of trial treatment.

The end of treatment visit is performed as close as possible (no longer than 5 calendar days) after a patient discontinues study medication permanently. The termination of trial medication form (eCRF page) must be completed for all patients who discontinue or complete the study regardless of reason. This includes patients who develop adverse events requiring permanent discontinuation of treatment on either stage of the protocol, or patients who were withdrawn for other reasons.

Perform investigations as defined by EOT instead of the scheduled visit when a patient discontinues study treatment permanently. If permanent discontinuation of study drug falls on a scheduled visit, examinations as defined for EOT should be performed instead of the examinations of the scheduled visit. Imaging and tumour assessment needs to be done only to diagnose/confirm progression or response.

Serum $\beta$ -HCG test (Pregnancy test)	For women of childbearing potential only
Echo or MUGA	Cardiac left ventricular function assessment (see section 5.2.10)
Physical examination	Including weight.
Cerebral MRI	Imaging and tumour assessment needs to be done only to diagnose/confirm progression or response. The EOT MRI/tumour assessments are optional if performed in the previous 4 weeks.
ECG	12-lead resting ECG will be performed
MMSE assessment	See Appendix 10.4
Karnofsky performance status	See Appendix 10.3
Concomitant therapy	Changes in concomitant medications will be documented
Vital signs	Temperature, blood pressure, pulse and respiratory rate after 2 min supine rest
Safety lab parameters	Hematology (including differential), biochemistry, and urine analysis (section 5.2.6).
Adverse events	Occurrence of adverse events since the last visit
Compliance check	The patient should bring his/her medication and the number of remaining tablets and capsules should be counted
Termination of study medication	

**Follow-up visit:** 28 days ( $\pm 4$ ) after EOT

Karnofsky performance status	See Appendix 10.3
Concomitant therapy	Changes in concomitant medications will be documented
Safety lab parameters	Hematology (including differential), biochemistry, and urine analysis (section 5.2.6).
Adverse events	Will be documented, if not recovered at EOT or new drug related AE

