-  Visit frequency will be as follows: every month for the first 6 months after RT (C1 to C6), every 2 months thereafter for the next six months (C8,C10,C12) and then every three months for the following year (C15,C18,C21, C24), and every 6 months thereafter (C30, C36.....). During the maintenance treatment phase visits should be performed as scheduled wherever possible, but within 2 days of the schedule date.
-  EOT: end of treatment visit; within 5 calendar days after permanent termination of trial drug intake. Investigations to be performed instead of the scheduled visit when a patient discontinues study treatment permanently. If permanent discontinuation of study drug falls on a scheduled visit, examinations as defined for EOT should be performed instead of the examinations of the scheduled visit.
-  FU: Follow-up visit: 28 days ( $\pm 4$ ) after EOT.
-  Early postoperative MRI (within 72 hours after initial surgery) preferable. In case a patient did not perform a Gd-enhanced MRI within 72 hours post surgery, a Gd-MRI is to be performed prior to start of study treatment MRIs should be performed between day 21 and day 28 of Cycle 2, 4, 6, 8, 10 and 12. In the second year, MRIs are performed every 3 months (Cycle 15, 18, 21, 24) and every six months thereafter (Cycle 30, 36...). The EOT MRI/tumour assessments are not required if performed in the previous 4 weeks.
-  For women of childbearing potential only.
-  Same method (Echo or MUGA) must be performed throughout study.
-  Includes height (at screening only) and weight.
-  ECG will be performed at Cycle 2 and every 8 weeks thereafter until cycle 12 (Cycle 4, 6, 8, 10, 12.) and then every three months for the following year (C15, C18, C21, C24), and every 6 months thereafter (C30, C36.....).
-  MMSE will be repeated at Cycle 2, 4, 6, 8,10 ,12 and then every three months for the following year (C15, C18, C21, C24), and every 6 months thereafter (C30, C36.....).
-  Includes CBC, serum biochemistry, and urinalysis, see Section 5.2.6 for details.
-  If not recovered at EOT, or new drug related AE
-  For detailed timing refer to Section 5.5.1 and 10.1
-  RT should be performed between 2 weeks and 6 weeks post surgery

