## **5.2 SAFETY**

### **5.2.1 Adverse events**

Upon inclusion into the trial, the patient’s condition is assessed (e.g., documentation of history / concomitant diagnoses and diseases), and all relevant changes from baseline are noted subsequently.

AEs will be collected from the date of signature of informed consent number 2. Once the MTD in Regimen U is determined, AEs will be collected from the date of signature of informed consent number 3.

Patients will be required to report spontaneously any adverse events (AEs) as well as the dates of onset and end of these events. These include all events that affect the well-being of the patients irrespective their relatedness to the treatment. Specific questions will be asked wherever required or useful to more precisely describe an AE and to allow a grading according to CTCAE, Version 3 (R06-1666).

A carefully written record of all AEs shall be kept by the investigator in charge of the trial. Records of AEs shall include data on the date of onset, end date and CTCAE grading of the event as well as any treatment or action required for the event and its outcome.

Regular and continuing assessment of safety will be performed for both parts of the study as outlined in the Flow Chart of this protocol. A dose reduction scheme is provided in Section 4.1.4.1.2 for patients who experience specified adverse events and who, at the discretion of the investigator, could derive benefit from continuing treatment on the protocol.

Adverse events with an onset during therapy with trial medication or within 28 days after discontinuation of drug intake are considered as “on-treatment”. Adverse events which are not yet recovered at the EOT visit will be followed up until recovery or in case of persistence sufficient characterization of the toxic effects has been achieved and the investigator and

Boehringer Ingelheim agree not to pursue them further. Adverse events that occur more than 28 days after last administration of study drug will only be reported if they are considered drug- or trial procedure-related.

Definitions and requirements for documentation and reporting of AEs and serious adverse events (SAEs) are provided in Sections 8.4.1. A list of expected adverse events with BIBW 2992 can be found in the current version of the investigator brochure.

The EU prescribing information for Temozolomide (current SPC) will be used for assessment of international listedness/expectedness of temozolomide.

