## **8.4 PROCEDURES**

### **8.4.1 Adverse events**

An adverse event (AE) is defined as any untoward medical occurrence, including an exacerbation of a pre-existing condition, in a patient in a clinical investigation who received a pharmaceutical product. The event does not necessarily have to have a causal relationship with this treatment.

All adverse events occurring during the course of the clinical trial (i.e., from signing the informed consent number 2 or 3 onwards to follow up visit (28 days after EOT)) will be collected, documented and reported to the sponsor by the investigator according to the specific definitions and instructions detailed in the 'Adverse Event Reporting' section of the Investigator Site File.

A serious adverse event (SAE) is defined as any AE which results in death, is immediately life-threatening, results in persistent or significant disability / incapacity, requires or prolongs patient hospitalisation, is a congenital anomaly / birth defect, or is to be deemed serious for any other reason if it is an important medical event when based upon appropriate medical judgement which may jeopardise the patient and may require medical or surgical intervention to prevent one of the other outcomes listed in the above definitions.

BI has set up a list of AEs which are defined to be always serious. In order to support the investigator with the identification of these "always serious adverse events", if a non serious AE is identified to be serious per BI definition, a query will be raised. The investigator must verify the description and seriousness of the event. If the event description is correct, the item "serious" needs to be ticked and an SAE has to be reported in expedited fashion following the same procedure as above. The list of these adverse events can be found via the RDC-system.

Progressive disease will not be recorded as an SAE if it is considered the natural course of the malignant disease but it will be recorded in the eCRF as outcome. Signs and symptoms of progressive disease may be reported as an AE (for details see Section 5.2.2)

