All adverse events, serious and non-serious, will be fully documented on the appropriate eCRFs. For each adverse event, the investigator will provide the onset, end, intensity, treatment required, outcome, seriousness and action taken with the investigational drug. The investigator will determine the relationship of the investigational drug to all AEs as defined in the 'Adverse Event Reporting' Section of the Investigator Site File.

The basis for judging the intensity of the AE has to follow the criteria laid out in the common terminology criteria for adverse events (CTCAE Version 3, R04-0474).

In addition the intensity of the SAE is also described as below.

Intensity of event

- Mild: Awareness of sign(s) or symptom(s) which is/are easily tolerated
- Moderate: Enough discomfort to cause interference with usual activity
- Severe: Incapacitating or causing inability to work or to perform usual Activities

The basis for judging the causal relationship between the investigational product at the AE is described below,

Causal relationship

Medical judgment should be used to determine the relationship, considering all relevant factors, including pattern of reaction, temporal relationship, de-challenge or re-challenge, confounding factors such as concomitant medication, concomitant diseases and relevant history. Assessment of causal relationship should be recorded in the case report forms.

- Yes: There is a reasonable causal relationship between the investigational drug administered and the AE.
- No: There is no reasonable causal relationship between the investigational drug administered and the AE.

If a SAE is reported from a still blinded trial, the causal relationship must be provided by the investigator for all potential trial drugs, i.e. the BI trial drug and for all other trial drugs (i.e. any active comparator or placebo according to the trial design).

The investigator has the obligation to report AEs/SAEs occurring between informed consent and the follow-up visit (28 days after EOT visit), regardless of causality. Adverse events that occur more than 28 days after last administration of study drug will only be reported if they are considered drug- or trial procedure-related. Deaths occurring after the follow-up visit (28 days after EOT visit) do not need to be reported as SAEs unless considered related to study treatment or procedures. Any AEs reported to the sponsor during this phase must be documented in the safety database.

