6. GENERAL ANALYSIS DEFINITIONS

6.1 TREATMENTS

For safety analyses, data up to and including 28 days after last treatment intake will be considered as on-treatment.

Patients will be analysed according to the treatment group initially assigned. All planned analysis will be presented by this treatment group. Handling of patients where treatment group assignment has not been followed will be handled on a case-by-case basis, to be agreed at report planning meetings.

Analyses for Regimen M and Regimen U will be presented separately.

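### The follow-up visit asks for fewer AEs than Section 8.4.1 and the SAP's 28-day on-treatment window, so new unrelated AEs after end of treatment may go unrecorded

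*Protocol*

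**What the plan says.** The visit schedule and the AE rules give different instructions for the time after EOT.

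- **Protocol 6.2.3, follow-up visit, adverse events row:** "Will be documented, if not recovered at EOT or new drug related AE". At every earlier treatment visit, including EOT, the row asks for any AE since the previous visit.
- **Flow charts, footnote 12 (both regimens):** "If not recovered at EOT, or new drug related AE".
- **Protocol 8.4.1, collection period:** all AEs from signing consent 2 or 3 "onwards to follow up visit (28 days after EOT)) will be collected, documented and reported to the sponsor".
- **Protocol 8.4.1, reporting duty:** "The investigator has the obligation to report AEs/SAEs occurring between informed consent and the follow-up visit (28 days after EOT visit), regardless of causality". The next sentence uses another end date: more than 28 days after the last administration, AEs "will only be reported if they are considered drug- or trial procedure-related".
- **Protocol 5.2.1:** events with onset on therapy or "within 28 days after discontinuation of drug intake are considered as" on-treatment. Reporting is limited to drug- or procedure-related events only after day 28.
- **SAP 6.1:** for safety analyses, "data up to and including 28 days after last treatment intake will be considered as on-treatment". SAP 7.8.1 assigns all AEs in that period to trial medication. Neither section has a relatedness condition.

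**The concern.** Incidence and intensity of AEs is the first secondary endpoint (protocol 2.3 and 5.1.2). The SAP analyses it mainly through tables of all treatment-emergent AEs, with related AEs in a separate table. If new events after EOT are entered only when the investigator judges them drug-related, the all-cause tables rest on two ascertainment rules: everything up to EOT, and a causality-filtered subset for most of the following four weeks. Any error goes one way, towards fewer events.

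An event that was never entered cannot be recovered at analysis, and its causality cannot be reassessed. Protocol 7.3.1 also lists events that meet the DLT criteria irrespective of relatedness, with study period at onset. A non-serious Grade 3 event after EOT that was judged unrelated could be missing from that listing. About five sites recruit competitively, and they may not all follow the same section.

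**Working it through.** No figure in the plan is in dispute. The check compares the rules and works out the time they affect.

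**Inputs.** EOT visit: 0 to 5 calendar days after last intake (protocol 6.2.3). Follow-up visit: 28 ± 4 days after EOT (6.1, 6.2.3). On-treatment window: to day 28 after last intake (5.2.1; SAP 6.1, 7.8.1).

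**Step 1: on-treatment time after EOT** = 28 − (EOT day).
- EOT on day 0: 28 − 0 = 28 days.
- EOT on day 5: 28 − 5 = 23 days.

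So 23 to 28 of the 28 post-treatment days fall after EOT. The follow-up visit is the only visit scheduled after EOT.

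**Step 2: day of the follow-up visit after last intake** = (EOT day) + 24 to (EOT day) + 32.
- EOT on day 0: day 24 to 32.
- EOT on day 5: day 29 to 37.

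The visit can therefore fall up to 4 days before day 28 (28 − 24) or up to 9 days after it (37 − 28). Between day 28 and a later follow-up visit, one sentence of 8.4.1 requires unrelated AEs and the next excludes them. The SAP assigns events in that interval to post-study.

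**Step 3: which events are exposed.**

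| Event after EOT, onset by day 28 | Kept under the follow-up row? | Kept elsewhere? |
|---|---|---|
| Present at EOT and not recovered | Yes | – |
| New, drug-related | Yes | – |
| New, unrelated, serious or significant | No | Yes: immediate reporting whatever the causality (8.4.1, 8.4.2) |
| New, non-serious, not judged drug-related | No | Only under 8.4.1 |

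The last line is the gap. It includes events related to a trial procedure but not to the drug, which 5.2.1 and 8.4.1 keep even after day 28. The follow-up row is thus narrower than the rule for the later period.

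**Step 4: illustrative size.** If one patient's event is missed and that patient is not otherwise counted under the term, incidence changes by 100/n points: 100/6 = 16.7, 100/12 = 8.3, 100/30 = 3.3.

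The documents give no rate for such events. Assume that a proportion q of patients have one and that every site follows the visit schedule. For an MTD cohort expanded to 12, the expected number of patients with an unrecorded event is 12q, and the chance of at least one is 1 − (1 − q)^12:

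| Assumed q | Expected patients | Chance of at least one |
|---|---|---|
| 5% | 0.6 | 46% |
| 10% | 1.2 | 72% |
| 20% | 2.4 | 93% |

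These are upper illustrations. SAP 7.8.1 counts patients, not events, so a patient already counted under the same term changes nothing unless the missed event has a higher grade.

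**The case against.** The strongest reply is that 8.4.1 states an express duty and refers sites to the AE reporting section of the Investigator Site File. A site that follows 8.4.1 loses nothing, and neither that file nor the eCRF is among the documents. The follow-up visit also records concomitant therapy changes and safety laboratory tests, which may prompt entry of some events. This stands: loss is conditional on sites following the visit schedule. It does not remove the conflict, because the schedule is part of the protocol and its row cannot be read as shorthand for 8.4.1.

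A reader might infer more than the documents support.

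- **That incidence is undercounted as a fact, or by a third.** For a patient stopping at Day 42, the smallest gap is 23 of 42 + 28 = 70 on-treatment days, or 33%. That is a share of calendar time, not of events, and it falls to 23/(365 + 28) = 6% for a patient treated for a year.
- **That only related events are collected after EOT.** Unresolved events are kept whatever their cause, and serious and significant events are reported separately.
- **That the MTD is affected.** A DLT must be related to BIBW 2992 (5.2.3), and the primary endpoint counts onset in the 42-day concomitant period (SAP 5.1).
- **That the related-AE results are inflated.** Related AEs have their own table, and SAP Section 7 bases percentages on all patients in the set by default. That table does not change.
- **That the endpoint itself is worded as all-cause with a fixed window.** Protocol 2.3 and 5.1.2 say neither. Those features come from 5.2.1 and the SAP.

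**Conclusion.** The inconsistency is real and should be corrected. Its consequence is limited. Where sites follow 6.2.3 and the flow charts, new non-serious AEs not judged drug-related, with onset between EOT and day 28, will not be recorded although the SAP counts them as on-treatment. All-cause AE incidence may then be undercounted. The exposed time is 23 to 28 days per patient. The number of events lost is unknown, because it depends on an event rate and on site practice that the documents do not give. The secondary safety tables are descriptive and no cohort comparisons are planned (protocol 7.3), so no formal inference is at stake. The DLT and MTD determination is essentially untouched.

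**What to change.** Reword the follow-up AE row in 6.2.3 and footnote 12 in both flow charts to: *AEs not recovered at EOT; all new AEs, whatever the causality, with onset up to 28 days after last intake; after that date, only AEs related to drug or trial procedure.* In 8.4.1, replace the end point of 28 days after EOT with 28 days after last intake, as 5.2.1 and the SAP already have it. State that when the follow-up visit falls before day 28, AEs up to day 28 remain reportable, since no later visit would collect them.

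Two simpler wordings do not work. An unqualified request for all AEs at follow-up would conflict with the day-28 limit when the visit falls on days 29 to 37. Restricting later events to drug-related ones would drop the procedure-related AEs that 5.2.1 and 8.4.1 keep.

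The cost is slightly more AE entry at a visit that already exists. Unrelated AEs between day 28 and a later follow-up visit would no longer be required, but the SAP already places these in post-study. The SAP needs no change.

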### 6.3 REMOVAL OF PATIENTS FROM THERAPY OR ASSESSMENT

A patient can be withdrawn from study treatment after discussion between the BI Clinical Monitor and the investigator.

A patient will be withdrawn from the study treatment:

- the patient is no longer able to participate in the study (e.g., AE, surgery, concomitant diagnoses, concomitant therapies or administrative reasons); in such a case the investigator's reason for a patient's removal must be recorded on the EOT page of the eCRF.
- significant deviation from the protocol or eligibility criteria; such patients will be considered protocol violations and removed from study.
- non-compliance with study or follow-up procedures.
- Patient not recovered from any DLT 14 days after the last administration of the study drugs. Recovery is defined as return to baseline level or CTCAE Grade 1, whichever is higher. Exception to this in patients who derive obvious clinical benefit according to the investigator's judgement could be considered upon discussion with BI's Clinical Monitor Local (CML). The dose reduction scheme provided in Table 4.1.4.1.2: 1 should be followed in this case.
- repeated episodes of drug related adverse reaction despite dose reductions
- documented progressive disease as defined in Section 5.1.3
- Cardiac left ventricular systolic dysfunction CTCAE Grade  $\geq 2$  at any time during the previous cycle or  $>20\%$  decline in the resting ejection fraction from baseline.

A patient will be withdrawn from the study if:

- patient withdrawal of consent and election to discontinue participation in the trial. Dates of patient withdrawal will be documented and the reason(s) for withdrawal recorded and discussed in the final study report.
- termination of the study by the sponsor

As soon as a patient is withdrawn from the trial, the next scheduled visit and the EOT have to be performed if feasible (not in case patient has withdrawn consent). Every effort should be made to follow-up patients in case an adverse event is still ongoing at the time of withdrawal.

The sponsor may remove patients from the study, after approval of amendment 5, if the patients have access to BIBW 2992 (Afatinib) through marketed product, an expanded-access program, named patient use program, compassionate use protocol or other means based on local regulation. If a patient is removed from the study, an end of treatment and follow up visit will need to be performed to ensure all adverse events are followed up. The cost of any on-going supply of BIBW 2992 (Afatanib) will be incurred by the Sponsor.

### **6.3.1 Replacement of patients**

Patients who do not receive study treatment during the chemoradiation phase for more than 5 consecutive days or more than 8 non-consecutive days for any reasons other than DLT will be replaced.

## **7. STATISTICAL METHODS AND DETERMINATION OF SAMPLE SIZE**

### **7.1 STATISTICAL DESIGN - MODEL**

This trial will use safety, pharmacokinetic and preliminary therapeutic effects of BIBW 2992 to identify the optimal dose to investigate in future studies. Cohorts of patients will be entered sequentially into escalating dosage tiers with the aim of establishing the optimal dosage of BIBW 2992 to administer in combination with TMZ in combination with radiotherapy in patients with newly diagnosed GBM with a methylated or unmethylated MGMT-promoter (regimen M). Cohorts of patients will also be entered sequentially into escalating dosage tiers with the aim of establishing the optimal dosage of BIBW 2992 to administer in combination with radiotherapy in patients with newly diagnosed GBM with an unmethylated MGMT-promoter (regimen U).

This "3+3" dose escalation design is conventional for Phase I oncology studies. This trial is open-labelled, which allows the safety of each dose of BIBW 2992 to be assessed before treating additional patients with higher doses. Patients will not be randomised; they will be assigned to the cohort that is being filled at the time the patient is ready to enter the trial.

The dose escalation procedure is described in Section 4.1.4.

